Grade 3	Interrupt dosing of encorafenib and binimetinib and refer subject to ophthalmologist within 7 days ^c : 
 If resolved to Grade ≤ 1 in ≤ 21 days, resume treatment at 1 reduced dose level^b of encorafenib and binimetinib. If not resolved to Grade ≤ 1 in ≤ 21 days, permanently discontinue encorafenib and binimetinib and close follow-up with ophthalmic monitoring until stabilization or resolution^c.
Grade 4	Permanently discontinue encorafenib and binimetinib and immediate follow-up with ophthalmic monitoring until stabilization or resolution ^c

Worst toxicity CTCAE, v.4.03 Grade (unless otherwise specified ^a)	Dose Modification for Encorafenib and for Binimetinib
Liver-Related Adverse Events	
Grade 1 AST or ALT > ULN to 3 × ULN	Maintain dose level of encorafenib and binimetinib.
Grade 2 AST or ALT > 3 to 5.0 × ULN or 3 × baseline value ^d AND blood bilirubin^g ≤ 2.0 × ULN	
Maintain dose level of encorafenib and interrupt dosing of binimetinib until resolved to Grade ≤ 1 (or Grade ≤ 2 in case of liver metastasis), then:
 
 • If resolved in ≤ 14 days, maintain dose level of encorafenib and binimetinib. • If not resolved in ≤ 14 days, interrupt dose of encorafenib (in addition to prior binimetinib) until resolved to Grade ≤ 1 (or Grade ≤ 2 in case of liver metastasis), then resume treatment at current dose level of encorafenib and 1 reduced dose level^b of binimetinib. 
If additional occurrence:
 
 • Interrupt dosing of encorafenib and binimetinib until resolved to Grade ≤ 1 (or Grade ≤ 2 in case of liver metastasis), then resume treatment at 1 reduced dose level^b of encorafenib and binimetinib. 
Treatment with encorafenib and binimetinib may be resumed sequentially at the Investigator's discretion, with encorafenib being resumed alone for one week before resuming binimetinib treatment.

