AST or ALT > 3.0 to 5.0 × ULN AND blood bilirubin ^g > 2.0 × ULN	
Interrupt dosing of encorafenib and binimetinib until resolved to Grade ≤ 1, then:
 
 • If resolved in ≤ 7 days, resume treatment at 1 reduced dose level^b of encorafenib and binimetinib. • If not resolved in ≤ 7 days, permanently discontinue encorafenib and binimetinib. 
Treatment with encorafenib and binimetinib may be resumed sequentially at the Investigator's discretion, with encorafenib being resumed alone for one week before resuming binimetinib treatment.

Grade 3 AST or ALT > 5.0 to 8.0 × ULN) AND blood bilirubin^g ≤ 2.0 × ULN	
Interrupt dosing of encorafenib and binimetinib until resolved to Grade ≤ 1 (or Grade ≤ 2 in case of liver metastasis), then:
 
 • If resolved in ≤ 14 days, resume treatment at current dose level of encorafenib and binimetinib. • If not resolved in ≤ 14 days, resume treatment at 1 reduced dose level^b of encorafenib and binimetinib. 
Treatment with encorafenib and binimetinib may be resumed sequentially at the Investigator's discretion, with encorafenib being resumed alone for one week before resuming binimetinib treatment.
 
If additional occurrence:
 
 • Interrupt dosing of encorafenib and binimetinib until resolved to Grade ≤ 1 (or Grade ≤ 2 in case of liver metastasis), then resume treatment at 1 reduced dose level^b of encorafenib and binimetinib.
AST or ALT >8 × ULN AND blood bilirubin ^g ≤ 2.0 × ULN	Permanently discontinue encorafenib and binimetinib.
AST or ALT > 5.0 × ULN AND blood bilirubin^g > 2.0 × ULN	Permanently discontinue encorafenib and binimetinib.

Worst toxicity CTCAE, v.4.03 Grade (unless otherwise specified ^a)	Dose Modification for Encorafenib and for Binimetinib
Grade 4 AST or ALT > 20.0 × ULN	Permanently discontinue encorafenib and binimetinib.
Cardiac Disorders - Left Ventricular Systolic Dysfunction^a (Dose Adjustment for Binimetinib ONLY).	

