Grade 4	Permanently discontinue encorafenib and binimetinib ^f

a : Not according to NCI-CTCAE

b : Dose reduction below 150 mg QD for encorafenib, and below 15 mg BID for binimetinib is not allowed.

c : Ophthalmic monitoring mandated for retinal events, posterior uveitis, RVO: further evaluation with specialized retinal imaging (e.g. ocular coherence tomography, fluorescein angiography). Any diagnosis of retinal events must be supported by presence or absence of symptoms, visual acuity assessment and findings in OCT.

d : For subjects enrolled with liver metastases and baseline LFT elevations.

e : Disorder characterized by redness, marked discomfort, swelling, and tingling in the palms of the hands or the soles of the feet.

f : A subject with a Grade 4 AE may resume treatment at the lower dose level if the AE recovers to Grade ≤ 1 within 28 days of discontinuing drug and, if in the opinion of the Investigator and Sponsor Medical Monitor, the event is not life-threatening and the subject can be managed and monitored for recurrence of AE. Any subjects requiring a treatment interruption of duration > 28 days must discontinue study drug permanently.

g : Refers to total bilirubin.

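### In the Grade 2 liver row of Table 14, the binimetinib hold for subjects with liver metastases can end at the moment it begins (minor, safety only)

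*Protocol*

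**What the plan says.** The rules are in Protocol Section 6.5.4.1, Table 14, under liver-related adverse events.

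- **Grade 1** is "AST or ALT > ULN to 3 × ULN"; both drugs continue.
- **Grade 2** is "AST or ALT > 3 to 5.0 × ULN or 3 × baseline value", with total bilirubin at most 2 x ULN. Footnote d limits the baseline criterion: "For subjects enrolled with liver metastases and baseline LFT elevations".
- **First Grade 2 event:** keep encorafenib and "interrupt dosing of binimetinib until resolved to Grade ≤ 1 (or Grade ≤ 2 in case of liver metastasis), then" go on at the same doses if recovery takes 14 days or less.
- **Grade 2 event lasting longer:** "If not resolved in ≤ 14 days, interrupt dose of encorafenib (in addition to prior binimetinib) until resolved to Grade ≤ 1", again with the liver-metastasis alternative in parentheses. Encorafenib then restarts at the same dose and binimetinib one level lower.
- **Additional Grade 2 occurrence:** "Interrupt dosing of encorafenib and binimetinib until resolved to Grade ≤ 1 (or Grade ≤ 2 in case of liver metastasis), then resume treatment" one level lower for both drugs.
- **Grade 3** begins at "AST or ALT > 5.0 to 8.0 × ULN" with the same bilirubin limit. Its instruction carries the same parenthetical: "Interrupt dosing of encorafenib and binimetinib until resolved to Grade ≤ 1 (or Grade ≤ 2 in case of liver metastasis), then" a 14-day rule.

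The neighbouring row, with the same enzyme range but bilirubin above 2 x ULN, requires Grade 1 or lower and makes no exception for liver metastases. Neither the Grade 2 row nor footnotes b, d and g set a minimum hold.

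**The concern.** A release point has to lie below the value that triggered the hold. In the Grade 2 row, the alternative for liver metastases is the grade that defines entry to the row. Followed literally, the instruction orders an interruption whose end condition is true when it starts.

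The alternative depends only on having liver metastases. Unlike footnote d, it does not ask for raised baseline liver tests. It therefore covers a subject whose AST and ALT were normal at entry and whose rise on treatment is judged drug-related, which is the situation the hold exists for.

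What is at stake is how drug-related liver toxicity is handled in this subgroup. At the same enzyme values, a subject without liver metastases stops binimetinib until recovery, while one with liver metastases may stay on full dose. Section 4.1 applies the same dose-modification recommendations in the Study extension period, so the wording stays in force although the last enrolled subject started treatment on 27 Dec 2019.

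**Working it through.** The plan gives no figure to reproduce. The check compares each entry value with the row's own release points.

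**Inputs (Table 14 unless stated).** Grade 1 is above 1 and up to 3 x ULN. Grade 2 is above 3 and up to 5 x ULN, or 3 x baseline under footnote d. Grade 3 is above 5 and up to 8 x ULN with bilirubin at most 2 x ULN. Release is at Grade 1 or lower (at most 3 x ULN) or, with liver metastases, at Grade 2 or lower (at most 5 x ULN). Dose levels are from Table 8.

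**Step 1: entry on the ULN criterion.**

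| AST/ALT at entry (x ULN) | Grade | At most 3 x ULN? | At most 5 x ULN? | Fall needed to reach 3 x ULN |
|---|---|---|---|---|
| 3.5 | 2 | no | yes | 1 − 3/3.5 = 14% |
| 4.0 | 2 | no | yes | 1 − 3/4 = 25% |
| 4.5 | 2 | no | yes | 1 − 3/4.5 = 33% |
| 5.0 | 2 | no | yes | 1 − 3/5 = 40% |

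With liver metastases the release point is met at entry in every case, so the required hold is 0 days. Without them, the hold lasts until the fall in the last column has occurred.

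**Step 2: the 14-day step.** It applies only if the release point is still unmet after 14 days. With liver metastases, that requires a value above 5 x ULN, which belongs to the Grade 3 row. While AST/ALT stays at or below 5 x ULN, the step cannot be reached.

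**Step 3: additional occurrence.** The hold on both drugs ends at once for the same reason, and the one-level reduction follows. From the starting doses, encorafenib goes from 300 to 225 mg once daily (225/300 = 0.75, −25%) and binimetinib from 45 to 30 mg twice daily (30/45 = 0.67, −33%).

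**Step 4: entry on the 3 x baseline criterion.** The trigger exceeds 5 x ULN when baseline exceeds 5/3 = 1.67 x ULN.

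| Baseline (x ULN) | 3 x baseline | Release point met at the trigger value? |
|---|---|---|
| 1.3 | 3.9 | yes |
| 1.66 | 4.98 | yes |
| 2.0 | 6.0 | no |
| 2.5 | 7.5 | no |

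Above 5 x ULN, the stricter rows govern, because Section 6.5.4 bases modifications on the worst toxicity so far. The problem does not extend to those entries.

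**Step 5: the Grade 3 row.** Entry is above 5 x ULN and release is at most 5 x ULN, so the same parenthetical is a real step down there.

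**The case against.** The strongest defence is that the 5 x ULN tolerance was intended. Inclusion criterion 12 lets subjects with liver metastases start at full dose with AST/ALT up to 5 x ULN. The parenthetical appears three times in the Grade 2 row and twice in the Grade 3 row, and it is dropped when bilirubin exceeds 2 x ULN. That is a coherent policy on isolated transaminase rises. It does not explain this row, however. If no hold was wanted, the row would say to continue, as the Grade 1 row does, and the 14-day step would have no purpose.

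Table 14 is headed as recommendations, so an investigator may hold for longer. That is true, but the text sets no length to work from. The one-level reduction at an additional occurrence does still protect the subject, and escalation above 5 x ULN is intact.

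A reader might infer that a rise found on Day 1 can run a full 28-day cycle with no retest called for, since from Cycle 2 chemistry is scheduled only on Day 1 (Sections 9.1.7 and 9.2.2). The documents do not support that. Section 10.1.1 says abnormal laboratory results meeting the adverse event criteria should be repeated until normal or stable, at a frequency the investigator sets, and it counts values needing a dose modification among them. The 28 days are only the interval between scheduled draws. Repeat testing does not cure the release point, though: a repeat at 4.5 x ULN still satisfies it.

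It is also argued that tightening the row would turn noise into holds, for example a baseline of 4.8 and a value of 4.9 x ULN judged drug-related. The cost is real, but if the ULN criterion is applied to such a subject, the present text already orders an interruption and, on recurrence, reduces both drugs.

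**Conclusion.** Wrong as written, minor, and confined to safety. For a subject with liver metastases whose drug-related AST/ALT lies above 3 and up to 5 x ULN with bilirubin at most 2 x ULN, the binimetinib hold has a required length of 0 days, the step beyond 14 days is unreachable while values stay in that range, and an additional occurrence reduces both drugs with no effective hold.

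This rests on a literal reading of the row and on Table 14's own grade bands. It covers subjects with normal baseline tests. It does not cover entry by 3 x baseline at values above 5 x ULN, the Grade 3 row's own step down, or the rows with bilirubin above 2 x ULN.

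A reader might also infer that many subjects were left at risk or that the trial's conclusions are affected. The documents do not give the number of subjects affected, and nothing in alpha, power or sample size depends on this row.

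**What to change.** In all three instructions of the Grade 2 row, replace the liver-metastasis alternative with a return to baseline level, if higher, for subjects enrolled with liver metastases and baseline LFT elevations. Everyone else uses Grade 1 or lower. The release point is then 3 x ULN, or the baseline where that lies above 3 and up to 5 x ULN, the most that eligibility allows. Footnote d already describes the group, and Table 14 already uses a baseline recovery point for other Grade 3 events.

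Make the same replacement in both instructions of the Grade 3 row (above 5 to 8 x ULN). If that row stayed as it is, a subject with liver metastases and normal baseline who peaked at 6 x ULN could restart both drugs at 4.5 x ULN, while one who peaked at 4.5 x ULN would have to wait for 3 x ULN. The worse event would get the easier restart. Leave the rows for values above 8 x ULN and for bilirubin above 2 x ULN unchanged.

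The cost is amended wording, site retraining, and some missed doses, hence lower dose intensity, in subjects with liver metastases. Some of them will also reach the steps for events lasting more than 14 days. The repeat tests needed to end a hold are already called for by Section 10.1.1.

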Asymptomatic absolute decrease of > 10% in LVEF compared to baseline and the LVEF is below the institution's LLN (e.g., a decrease of 60% to 48% is an absolute decrease of 12%)	Interrupt dosing of binimetinib and repeat evaluation of LVEF within 2 weeks. 
 If the LVEF recovers (defined as LVEF ≥ 50% or ≥ lower limit of normal (LLN) and absolute decrease ≤ 10% compared to baseline) ≤ 21 days, resume treatment at 1 reduced dose level^b of binimetinib after approval of the Sponsor's Medical Monitor. Monitor LVEF 2 weeks after resuming binimetinib, every 4 weeks for 12 weeks and subsequently as per protocol. If LVEF does not recover in ≤ 21 days, permanently discontinue binimetinib. Closely monitor LVEF until resolution or for up to 16 weeks.
Grade 3 – 4	Permanently discontinue binimetinib. Closely monitor LVEF until resolution or up to 16 weeks. Note: Copies of ECHO and/or MUGA scans could be requested for subjects to be available to the Sponsor for subjects with absolute decrease of >10% in LVEF compared to baseline and LVEF < 50% or LLN.
CK Elevation	
Grade 1-2	Maintain dose of encorafenib and binimetinib. Ensure subject is adequately hydrated. Closely monitor CK and serum creatinine. 
 If total CK ≥ 3 × ULN, measure CK isoenzymes and myoglobin in blood or urine.
Grade 3 > 5.0 - 10.0 × ULN without renal impairment (i.e., serum creatinine < 1.5 × ULN or 1.5 × baseline)	If asymptomatic, maintain dosing of encorafenib and binimetinib. Ensure subject is adequately hydrated. Monitor and measure isoenzymes and myoglobin in blood or urine and serum creatinine. If symptomatic (muscle pain/spasms/muscle weakness), maintain dosing of encorafenib and interrupt dosing of binimetinib until resolved to CTCAE Grade ≤ 1 and monitor closely, then: 
 If resolved in ≤ 21 days, maintain dose of encorafenib and resume treatment at 1 reduced dose level^b of binimetinib. If not resolved in ≤ 21 days, maintain dose of encorafenib and permanently discontinue binimetinib.

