Grade 4 without renal impairment (i.e., serum creatinine < 1.5 × ULN or 1.5 × baseline)	If asymptomatic, maintain dose of encorafenib and interrupt dosing of binimetinib. Ensure subject is adequately hydrated. Monitor and measure isoenzymes and myoglobin in blood or urine and serum creatinine. 
 If resolved in ≤ 21 days, maintain dose of encorafenib and resume treatment at 1 reduced dose level^b of binimetinib. If not resolved in ≤ 21 days, maintain dose of encorafenib and permanently discontinue binimetinib. If symptomatic (muscle pain/spasms/muscle weakness), maintain dose of encorafenib and permanently discontinue binimetinib.
Grade 3 or 4 with renal impairment (i.e., serum creatinine ≥ 1.5 × ULN or 1.5 × baseline)	Interrupt dosing of encorafenib and binimetinib until resolved to CTCAE Grade < 1 or baseline level. Ensure subject is adequately hydrated. Monitor closely and measure isoenzymes and myoglobin in blood or urine and serum creatinine, then: 
 If resolved in ≤ 21 days, consider resuming treatment at 1 reduced dose level^b of encorafenib and binimetinib. If not resolved in ≤ 21 days, permanently discontinue encorafenib and binimetinib. 2 nd occurrence: 
 Permanently discontinue encorafenib and binimetinib.

Worst toxicity CTCAE, v.4.03 Grade (unless otherwise specified ^a)	Dose Modification for Encorafenib and for Binimetinib
Cardiac Investigation – Prolongation of QT interval QTcF value	

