QTcF > 500 ms during treatment and change from pre-treatment value remains ≤ 60 ms	
Subjects should have regular ECG monitoring (continuous where appropriate) until an adequately trained physician (such as a cardiologist or internist) has reviewed the data. Electrolyte abnormalities including magnesium should be corrected and cardiac risk factors for QT prolongation (e.g., congestive heart failure, bradyarrhythmias) should be controlled.
 
1st occurrence:
 
 Temporarily interrupt dosing of encorafenib and binimetinib until QTcF < 500 ms. Then resume treatment at 1 reduced dose level^b of encorafenib and binimetinib. 
2nd occurrence:
 
 Temporarily interrupt dosing of encorafenib and binimetinib treatment until QTcF < 500 ms. Then resume treatment at 1 reduced dose level^b of encorafenib and binimetinib. If a subject restarts binimetinib and encorafenib following resolution of Grade 3 QTcF prolongation event, the subject should be evaluated with triplicate predose ECGs on Day 1 of the next cycle, followed by a single postdose ECG and a single predose ECG on Day 15, as well as single predose ECG and a single postdose ECG on Day 1 of the subsequent cycle (2nd cycle after the Grade 3 QT prolongation event). 
3rd occurrence:
 
 Permanently discontinue encorafenib and binimetinib.
QTcF increase during treatment is both > 500 ms and > 60 ms change from -pretreatment values	
Subjects should have regular ECG monitoring (continuous where appropriate) until an adequately trained physician (such as a cardiologist or internist) has reviewed the data. Electrolyte abnormalities including magnesium should be corrected and cardiac risk factors for QT prolongation (e.g., congestive heart failure, bradyarrhythmias) should be controlled.
 
 Permanently discontinue encorafenib and binimetinib.
Rash [see cetuximab dose modifications (Table 15) and (Section 17.1).	
Grade 1	
Maintain dose level of encorafenib and binimetinib. Initiate Initial Rash Treatment Regimen (see Section 17.1. if it was not already started and rash should be closely monitored).

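### Table 14, CK elevation: the rows without and with renal impairment both join their limits by an or, so they overlap and give conflicting first dose instructions; a minor safety correction

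*Protocol*

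**What the plan says.** The CK block of Protocol Table 14 (section 6.5.4.1) splits Grade 3 and Grade 4 events by renal function.

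- Grade 3, no impairment: CK "without renal impairment (i.e., serum creatinine < 1.5 × ULN or 1.5 × baseline".
- Grade 4, no impairment: "Grade 4 without renal impairment (i.e., serum creatinine < 1.5 × ULN or 1.5 × baseline".
- Either grade, with impairment: "Grade 3 or 4 with renal impairment (i.e., serum creatinine ≥ 1.5 × ULN or 1.5 × baseline".

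The rows without impairment also split by symptoms, which gives four branches. All four keep encorafenib going. For binimetinib they say maintain (Grade 3 asymptomatic), interrupt (Grade 3 symptomatic), interrupt (Grade 4 asymptomatic) and, for Grade 4 symptomatic, "If symptomatic (muscle pain/spasms/muscle weakness), maintain dose of encorafenib and permanently discontinue binimetinib". The row with impairment has a single opening action whatever the symptoms: "Interrupt dosing of encorafenib and binimetinib until resolved to CTCAE Grade < 1 or baseline level".

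No Table 14 footnote says which creatinine limit governs or which CK row prevails. The general rule in section 6.5.4, that modifications follow the worst preceding toxicity, does not define renal impairment.

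**The concern.** The labels present the rows as two halves of a partition, but the definitions in brackets do not form one. The opposite of reaching either limit is being below both, whereas the rows without impairment ask only for being below one or the other. A subject whose baseline creatinine differs from the ULN can therefore have a value that satisfies both definitions, and the table gives that subject two different orders.

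The stake is what happens to the two oral drugs. The rows also diverge after the first step. If CK has not resolved by 21 days, the row with impairment stops both oral drugs for good, while the rows without impairment keep encorafenib. Section 6.5.4 takes subjects off study treatment if they cannot continue on at least two of the agents, so the row chosen can decide whether someone stays on encorafenib plus cetuximab. In the other direction, an asymptomatic Grade 3 CK with a clear rise in creatinine can be read as permitting both drugs to continue unchanged.

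**Working it through.** The plan states no figure on this point, so there is none to reproduce. The check is logical.

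**Inputs.** U is the ULN for creatinine, B the subject's baseline and c the current value. The definitions and actions are from Table 14, CK Elevation. Inclusion criterion 10 (section 5.1) accepts creatinine up to 1.5 × ULN or a calculated clearance of at least 50 mL/min, so B may lie below or above U.

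**Step 1: the literal definitions.**
- Without impairment: c < 1.5U or c < 1.5B, which is the same as c < max(1.5U, 1.5B).
- With impairment: c ≥ 1.5U or c ≥ 1.5B, which is the same as c ≥ min(1.5U, 1.5B).
- Both hold when min(1.5U, 1.5B) ≤ c < max(1.5U, 1.5B). This range is empty only if B = U. No value falls in neither row.

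**Step 2: the size of the overlap**, in multiples of ULN, for assumed baselines:

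| Baseline (× ULN) | 1.5 × baseline | Creatinine meeting both rows |
|---|---|---|
| 0.6 | 0.90 | 0.90 to < 1.50 |
| 0.8 | 1.20 | 1.20 to < 1.50 |
| 1.0 | 1.50 | none |
| 1.2 | 1.80 | 1.50 to < 1.80 |
| 1.6 (clearance limb only) | 2.40 | 1.50 to < 2.40 |

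An enumeration over 7 ULN values, 18 baselines and 370 creatinine values (7 × 18 × 370 = 46,620 combinations) put 9,129 in both rows and 0 in neither, with no departure from the Step 1 range. This tests the logic; it is not a frequency among subjects.

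**Step 3: first instruction, without versus with impairment.**

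| Branch | Encorafenib | Binimetinib |
|---|---|---|
| Grade 3 asymptomatic | maintain vs interrupt | maintain vs interrupt |
| Grade 3 symptomatic | maintain vs interrupt | interrupt in both |
| Grade 4 asymptomatic | maintain vs interrupt | interrupt in both |
| Grade 4 symptomatic | maintain vs interrupt | permanent stop vs interrupt |

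Encorafenib conflicts in 4 of 4 branches and binimetinib in 2 of 4, so 6 of 8 first instructions differ. In 7 of 8 the row with impairment is as strict or stricter. The exception is binimetinib in symptomatic Grade 4, where the row without impairment is stricter.

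**Step 4: the correction.** Define without impairment as c < 1.5U and c < 1.5B, that is, c < min(1.5U, 1.5B). This is the exact complement of the row with impairment. On the same 46,620 combinations, 0 fell in both rows and 0 in neither.

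**The case against.** The best reply is that nobody would read the table this way. The rows are labelled as opposites, and a clinician who sees impairment defined as reaching either limit would normally take its absence to mean that neither is reached. The rule on worst preceding toxicity also leans towards the row with impairment. Much of this stands, and it limits the practical effect. It does not make the stated definition right, and leaning on the worst toxicity does not settle symptomatic Grade 4, where the other row is the stricter one for binimetinib.

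Several stronger readings are tempting and should not be drawn.

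- *That the or is deliberate because Table 14 marks conjunctions explicitly.* It does so in "QTcF increase during treatment is both > 500 ms and > 60 ms change from -pretreatment values" and in "AST or ALT > 5.0 × ULN AND blood bilirubin", but those join different quantities. Where the table gives two reference limits for one measurement, as in the LVEF rows (50% and the lower limit of normal), it uses the same loose or. The CK wording looks like shorthand.
- *That sites hold two rival interpretations, one applying the baseline limit only when baseline is abnormal.* The liver rows do this in "AST or ALT > 3 to 5.0 × ULN or 3 × baseline value", through footnote d, which concerns liver metastases and raised baseline liver tests. The CK rows carry no such footnote, so nothing shows that sites would read them that way.
- *That about 9 of 90 subjects are exposed.* Table 6 reports Grade 3/4 CK in 3 of 30 in the triplet lead-in (3/30 × 90 = 9) and raised creatinine in 8 of 30. The lead-in enrolled previously treated patients, the table does not say whether the two events coincided, and the scaling counts everyone with high CK over a whole trial. It does not count subjects in the overlap under this version.

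**Conclusion.** The definitions overlap as written. For Grade 3 or 4 CK with creatinine between 1.5 × ULN and 1.5 × baseline, the first instructions contradict each other for encorafenib in every branch and for binimetinib in asymptomatic Grade 3 and symptomatic Grade 4. This rests on reading the or literally and comparing first instructions only.

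It is a minor safety correction. The table is headed as recommendations, and section 6.5.4.1 says doses may be adjusted. The rows call for hydration and monitoring, and Table 20 footnote b adds weekly CK follow-up for asymptomatic Grade 3. This version is dated 17 July 2020 and the last subject started on 27 December 2019, so only subjects still on treatment are concerned; CK is not in the extension-period laboratory panel (Table 21). The number affected cannot be derived from the documents. A reader might infer that subjects were in fact handled inconsistently, or that the response-rate result is in doubt. The documents give no evidence of the first, and the primary analysis does not depend on these rows.

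**What to change.** Reword three cells of Table 14.

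- Grade 3 and Grade 4 rows without impairment: *serum creatinine < 1.5 × ULN and < 1.5 × baseline*.
- Row with impairment: *serum creatinine ≥ 1.5 × ULN or ≥ 1.5 × baseline*.

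The actions stay as they are. A site letter would suffice; sample size, visits and analysis are unaffected. There is one small downside. A subject whose creatinine rises to 1.5 × baseline while still within normal limits (for example, from 0.6 to 0.9 × ULN) is then managed in the row with impairment, with both oral drugs interrupted.

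Two clinical questions should be put to the sponsor's clinicians separately, outside this correction.

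1. Should symptomatic Grade 4 CK with renal impairment also stop binimetinib permanently? If so, it must be written as an exception to that row's option to consider resuming treatment, or it creates a new conflict.
2. How should subjects with baseline creatinine already at or above 1.5 × ULN be classified? They meet the impairment definition without any change in creatinine.
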